4.1.5 Evaluation of Toxicity and Response

- For dose escalation purposes, the DLT evaluation period is defined as the first 10 weeks of treatment (ie, 6 weeks of CRT plus LC followed by a 4-week post-CRT period).
 - Patients are available for DLT evaluation if they have either:
 - Received at least 80% of the planned doses of LC (8 of the planned 10 doses), at least 80% of the planned RT, and at least 60% of the planned TMZ
- OR

- Experienced a DLT in the first 10 weeks of treatment
- Dose finding will be performed using a TITE-BOIN schema as outlined in [Section 8.4.9](#). The window for DLT evaluation and decisions regarding dose advancement or de-escalation will be based on events occurring during the first 10 weeks of the study, though further data regarding safety and tolerability will be collected on every patient continuing infusions through the adjuvant TMZ treatment period.
- Standard contrast magnetic resonance imaging (MRI) will be used for assessment of progression, following the Response Assessment in Neuro-Oncology (RANO) criteria for PD. Patients will have a baseline MRI study followed by CRT, an MRI at the beginning of the adjuvant TMZ phase (4 weeks after completion of CRT) and another MRI every 2 cycles thereafter as per standard of care. More frequent imaging may be clinically necessary per the discretion of the treating physicians.
- MRI scans will be assessed locally by board-certified neuroradiologists who will independently assess tumor size and radiographic changes.
- For the first 2 years after the last dose of LC, patients will be followed for survival and progression every 2 months by telephone call, clinic visit, or medical records. After 2 years have elapsed, patients will be followed every 6 months for survival and progression by telephone call, clinic visit, or medical records.
- For the purposes of analyses, the duration of each arm will last through the 6 weeks of CRT, the 4-week post-CRT period, and the adjuvant cycles received by the patient.

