7.2.1.1 Adverse Event Description and Grade

The descriptions and grading in the NCI CTCAE version 5.0 will be used in the reporting of AEs. A change in grade will be reported as a separate AE. A copy of the CTCAE v 5.0 may be downloaded from

http://ctep.cancer.gov/protocolDevelopment/electronic_applications/ctc.htm.

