8.3 Populations for Analyses

For purposes of analysis, the following populations are defined:

Table 9. Populations for Analysis

Population	Description
Enrolled	All patients who sign the ICF
Evaluable (Escalation Phase)	All escalation patients who receive at least 80% of the planned doses of LC, 80% of planned RT, and 60% of planned TMZ in the first 10 weeks or experience a DLT prior to receiving 10 doses of LC
Efficacy Evaluable (Expansion Phase)	All expansion patients who receive at least 1 dose of LC and have baseline and at least one post-baseline tumor assessment.
Safety	All patients who receive at least 1 dose of LC. Patients will be analyzed according to the dose level they actually receive.

DLT = dose-limiting toxicity; ICF = Informed Consent Form; LC = liposomal curcumin; RT = radiation therapy; TMZ = temozolomide

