All safety analyses will be performed on the Safety Population. Safety analyses will be presented by dose level and overall. Separate safety analyses for the escalation and expansion phases may be generated for patients treated at the MTD for select safety endpoints.

Safety endpoints include DLTs, AEs, changes in laboratory values, ECGs, and changes in vital signs. All AE terms will be coded using MedDRA preferred term and system organ class.

The proportion of patients experiencing at least 1 DLT as well as the number of DLTs observed will be summarized using frequency table techniques; Exact 95% confidence intervals may be generated. Adverse events occurring after the first study intervention will be summarized as follows: all AEs, SAEs, AEs related to study drug, AEs by severity, AEs by grade using CTCAE, and AEs leading to death.

Laboratory and vital sign data will be summarized as continuous variables by dose level and time point. Changes from baseline will be presented along with observed value at each time point. Select laboratory parameters may be graded using CTCAE. Grades for these lab parameters will be summarized in shift tables comparing the baseline grade to the maximum observed post-baseline grade.

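### Section 8.4.6 reports the DLT proportion on the Safety Population, so patients who leave before week 10 without a DLT dilute it; dose decisions use a different denominator

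*Protocol*

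**What the plan says.** Section 8.4.6 sets the population without exception: "All safety analyses will be performed on the Safety Population". It continues: "Safety endpoints include DLTs, AEs, changes in laboratory values, ECGs, and changes in vital signs". It then fixes the summary: "The proportion of patients experiencing at least 1 DLT as well as the number of DLTs observed will be summarized using frequency table techniques", with exact 95% confidence intervals optional.

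Table 9 in Section 8.3 defines the Safety Population as "All patients who receive at least 1 dose of LC", with no follow-up requirement. The same table defines an Evaluable population for the escalation phase only: "All escalation patients who receive at least 80% of the planned doses of LC, 80% of planned RT, and 60% of planned TMZ". These thresholds apply to the first 10 weeks, and a DLT also qualifies a patient. Section 4.1.5 applies the same thresholds, introduced by "Patients are available for DLT evaluation if they have either". Figure 2 and Table 10 in Section 8.4.9 use evaluable patients at the current dose as the denominator for dose decisions.

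Section 8.4.8 gives the yardstick: a 10-week window, a target DLT risk of 30% with range 23.6% to 35.9%, and 20%, 30% and 50% of the risk placed in successive thirds of the window.

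**The concern.** The design targets the risk that a patient has a DLT within 10 weeks. A patient who has one infusion and leaves in week 2 says little about that risk, least of all when half of it is placed in the last third of the window. Section 8.4.6 nevertheless gives that patient the same weight as one observed for all 10 weeks without a DLT.

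The reported proportion then differs from the rate used to choose the dose, and it errs towards looking safer. Readers of the final report, including those planning the next trial, would naturally compare it with 30%. Expansion patients add to the problem. Section 8.6 monitors them against the same 30% risk, but Table 9 gives them no DLT-evaluable set.

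**Working it through.** **The plan's own figure.** The interval boundaries follow from target φ = 0.30 with φ1 = 0.6φ = 0.18 and φ2 = 1.4φ = 0.42. These multipliers are the usual defaults and are assumed here, since the protocol does not state them.

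- Lower: ln[(1−φ1)/(1−φ)] / ln[φ(1−φ1)/(φ1(1−φ))] = 0.2365
- Upper: ln[(1−φ)/(1−φ2)] / ln[φ2(1−φ)/(φ(1−φ2))] = 0.3585

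This agrees with the stated range of 23.6% to 35.9%. With nobody pending, the de-escalation cut-offs (2/3, 3/6, 4/9, 5/12) and elimination cut-offs (3/3, 4/6, 5/9, 7/12) also match Table 10. The yardstick is sound; the question is which denominator is held against it.

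**Share of risk passed by a leaver.** Under the 20/30/50 split, the average cumulative share is 0.10 in the first third, 0.35 in the second and 0.75 in the last. If leaving times are uniform over 10 weeks, the mean share is (0.10 + 0.35 + 0.75)/3 = 0.40.

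**Expected rates.** Let the true 10-week risk be 0.30 and let a fraction d leave, independently of DLT risk. The protocol gives no value for d, so 5 to 30% is an assumption.

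- Patients with an observed DLT: E = 0.30 × [(1−d) + 0.40d] = 0.30 × (1 − 0.6d). This is the expected Safety-Population proportion.
- Leavers without a DLT: d × (1 − 0.30 × 0.40) = 0.88d.
- Expected evaluable proportion, treating all of these as non-evaluable: E / (1 − 0.88d).
- Follow-up-weighted proportion, counting each leaver without a DLT as 0.40 of a patient (an approximation): E / [E + 0.70(1−d) + 0.88d × 0.40].

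| Leaving (assumed) | Safety | Shortfall from 30% | Evaluable | Follow-up-weighted |
|---|---|---|---|---|
| 5% | 29.1% | 0.9 | 30.4% | 29.9% |
| 10% | 28.2% | 1.8 | 30.9% | 29.8% |
| 20% | 26.4% | 3.6 | 32.0% | 29.5% |
| 30% | 24.6% | 5.4 | 33.4% | 29.2% |

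**Effect of timing.** If all of an assumed 20% leave at week 3.33, the Safety figure is 0.30 × (0.80 + 0.20 × 0.20) = 25.2%. At week 5, where 35% of the risk has passed, it is 0.30 × (0.80 + 0.20 × 0.35) = 26.1%.

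**One dose level.** Take 12 treated patients (exact 95% intervals in brackets).

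- 3 DLTs and 3 early leavers without a DLT: 3/12 = 25.0% (5.5 to 57.2) on the Safety Population, against 3/9 = 33.3% (7.5 to 70.1) on evaluable patients.
- 4 DLTs and 2 such leavers: 4/12 = 33.3% (9.9 to 65.1) against 4/10 = 40.0% (12.2 to 73.8). The two point estimates fall on opposite sides of 35.9%.

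**The case against.** The strongest reply is that this is one descriptive proportion in a study with no hypothesis test (Section 8.1). Its interval is optional, and Section 8.4 calls itself a high-level summary over which the SAP prevails. At these sample sizes the intervals above overlap almost entirely. Listings, population counts and the feasibility proportion would let a reader rebuild the other figure. All of that is true and limits the weight of the point. It does not remove it: Section 8.4.6 states a denominator, and it differs from the one in Sections 4.1.5 and 8.4.9.

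Non-evaluable also does not mean unobserved. A patient can miss the exposure thresholds and still be watched to week 10. Sections 4.1.6 and 7.2.2 follow adverse events for 30 days after the last LC dose, so a last dose on Day 36 gives follow-up to about Day 66. Section 6.1 counts from the last temozolomide dose as well, which can extend this. Such patients are largely or fully observed non-DLTs at reduced exposure. Conversely, someone who leaves after meeting all three thresholds is evaluable under Table 9. The table above simplifies both groups.

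A reader might infer several stronger things that the protocol does not support:

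- **That the dose decisions or the MTD are biased.** They are not biased by this sentence, because Figure 2 and Table 10 count evaluable patients.
- **That the Evaluable set has no use.** It drives dose finding, and Section 8.5 builds the feasibility estimate on the same thresholds.
- **That the primary endpoint is diluted.** Tables 1 and 3 list a count of DLTs, which no denominator changes.
- **That one episode is counted several times** because "A change in grade will be reported as a separate AE". That rule governs adverse event records. Nothing says DLTs are counted from those records, and Section 8.4.6 already reports patients with at least one DLT.
- **That the whole gap between the Safety and evaluable proportions is dilution.** The evaluable set keeps every DLT and drops only patients without one, so it is itself biased upward.

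**Conclusion.** The point holds for the reported proportion of patients with at least one DLT, and for its confidence interval if one is produced. As written, Section 8.4.6 counts a patient who leaves early without a DLT as a full non-event, and so understates the 10-week risk in expectation. Measured against a true risk of 30%, the expected shortfall is about 1 to 5 points for 5 to 30% leaving. It grows if patients leave earlier and vanishes if none do. These sizes rest on the assumed leaving fractions, uniform leaving times, leaving unrelated to DLT risk, and the protocol's own split of risk over the window. The SAP may already specify a different denominator, but the protocol text does not. The change is worth making because the error is in the direction of apparent safety and costs little to correct.

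**What to change.** - In Section 8.4.6, name the DLT analysis as an exception to the Safety-Population rule. Report by dose level the proportion of patients with at least one DLT within the 10-week window in a DLT-evaluable set, with an exact 95% confidence interval.
- In Table 9 (Section 8.3), extend the DLT-evaluable definition to expansion patients.
- Beside the main figure, show the Safety-Population proportion and a 10-week estimate that uses partial follow-up, either follow-up-weighted or Kaplan-Meier time to first DLT. Switching to the evaluable set alone would replace an understatement with an overstatement.

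The cost is wording in Sections 8.3 and 8.4.6, one extra table, and slightly wider confidence intervals. No change is needed to the escalation rule, the sample size or data collection.

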8.4.7 Efficacy Analyses

Overall survival will be estimated using the Kaplan-Meier method, with quartile estimates and associated 95% confidence intervals presented. Patients who are alive at the time of analysis will be censored at the last date that they were known to be alive (last study visit if the patient is still on treatment, or last long-term survival assessment where the patient was known to be alive).

Progression-free survival, defined as the time from the day of first study treatment to disease progression or death, whichever occurs first, will be estimated using Kaplan-Meier techniques based on RANO criteria. Patients without evidence of progression will be censored at their last tumor response assessment.

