Intervention Groups and Duration: The duration of treatment for each patient will be up to 34 weeks. Treatment starts with the beginning of infusion and ends, if tolerated, at the end of Cycle 6 of adjuvant TMZ.

Safety Review Committee: This study will be overseen by a Safety Review Committee (SRC) charged with evaluating dose escalations and monitoring safety data throughout the trial (Section 4.1.6).

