1.2 Schema

Figure 1. Study Design

IV = intravenous; MRI = magnetic resonance imaging; TMZ = temozolomide; XRT = radiation therapy
Treatment starts in first week of chemoradiation.

The DLT evaluation period is 10 weeks. Afterward, patients will continue adjuvant TMZ and LC for an additional 24 weeks.

Procedure	Baseline	CRT Period						Post-CRT				Adjuvant Cycles 1 - 6				End Of Treatment ¹⁴	LTFU	End of Study
		Week						Week				Adjuvant Week						
	≤14 Days of D1	1	2	3	4	5	6	7	8	9	10	1	2	3	4			
		D1	D8 ±3	D15 ±3	D22 ±3	D29 ±3	D36 ±3	D43 ±3	D50 ±3	D57 ±3	D64 ±3	D71 ±3	D78 ±3	D85 ±3	D92 ±3		±14 Days	
Clinical chemistry ³	X			X	X			X				X				X		
Complete urinalysis	X																	
Urine pregnancy test (WOCBP only) ⁶	X	X						X				X						
12-lead ECG ⁷	X				X							X						
Administration of RT ⁸		X	X	X	X	X	X											
Administration of TMZ/ondansetron ⁹		X	X	X	X	X	X					X						
Administration of LC/premedication ¹⁰		X	X	X	X	X	X	X	X	X	X	X	X	X	X			
Concomitant medications	X ¹¹	X	X	X	X	X	X	X	X	X	X	X	X	X	X	X		
Adverse events ¹²		X	X	X	X	X	X	X	X	X	X	X	X	X	X	X		X

Procedure	Baseline	CRT Period						Post-CRT				Adjuvant Cycles 1 - 6				End Of Treatment ¹⁴	LTFU	End of Study
		Week						Week				Adjuvant Week						
	≤14 Days of D1	1	2	3	4	5	6	7	8	9	10	1	2	3	4			
		D1	D8 ±3	D15 ±3	D22 ±3	D29 ±3	D36 ±3	D43 ±3	D50 ±3	D57 ±3	D64 ±3	D71 ±3	D78 ±3	D85 ±3	D92 ±3		±14 Days	
Overall survival and progression-free survival ¹³																	X	

CRT = chemoradiotherapy; ECG = electrocardiography; Hgb = hemoglobin; IV = intravenous; KPS = Karnofsky Performance Scale; LC = liposomal curcumin; LTFU = long-term follow-up; MRI = magnetic resonance imaging; PO = per os (oral); RT = radiotherapy; TMZ = temozolomide; WOCBP = women of childbearing potential

1. MRI: Performed at baseline (-21 days) prior to first study drug administration, before every odd-numbered adjuvant cycle (1, 3, 5, etc; approximately every 8 weeks), and at the discretion of the Investigator. End of Treatment MRI does not need to be repeated if performed within the 14 days prior to the End of Treatment date.
2. Vital signs: Include systolic and diastolic blood pressure, respiratory rate, heart rate, temperature, weight, and height. Height is required only at the baseline visit. Vital signs must be performed within 120 min of LC administration.

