7.3.4 Use of Criteria from Response Assessment in Neuro-Oncology for Assessment of Progression

Progressive disease is defined by *any* of the following:

- a) $\geq 25\%$ increase in sum of the products of perpendicular diameters of enhancing lesions compared to the smallest tumor measurement obtained either at baseline

- (if no decrease) or best response, on stable or increasing doses of corticosteroids. (Stable doses of corticosteroids include patients not on corticosteroids.)
- b) Significant increase in T2-fluid-attenuated inversion recovery (FLAIR) nonenhancing lesion on stable or increasing doses of corticosteroids compared to baseline scan or best response following initiation of therapy, not due to comorbid events (RT, demyelination, ischemic injury, infection, seizures, postoperative changes, or other treatment effects)
 - c) Any new lesion
 - d) Clear clinical deterioration not attributable to other causes apart from the tumor (eg, seizures, medication adverse effects, complications of therapy, cerebrovascular events, infection, etc) or changes in corticosteroid dose. A diagnosis of clinical progression or deterioration may be made at the discretion of the treating physician.
 - e) Failure to return for evaluation due to death or deteriorating condition
 - f) Clear progression of nonmeasurable disease

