7.3.6 Progression-free Survival

Progression-free survival is defined as the duration of time from the start of treatment with LC to the time of progression or death, whichever occurs first. For the first 2 years after the last dose of LC, patients will be followed for progression every 2 months by telephone call, clinic visit, or medical records. After 2 years have elapsed, patients will be followed every 6 months for progression by telephone call, clinic visit, or medical records.

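### PFS non-events are censored at the last tumor response assessment while progression and death still count in long-term follow-up, so as written the PFS curve after about 8 months is biased downward

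*Protocol*

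**What the plan says.** Protocol Section 8.4.7 describes PFS as "defined as the time from the day of first study treatment to disease progression or death, whichever occurs first", with no cut-off at the last scan or at the end of treatment. The censoring rule follows: "Patients without evidence of progression will be censored at their last tumor response assessment". The term for the censoring date is not defined.

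Footnote 1 to the Schedule of Activities places MRI at baseline, "before every odd-numbered adjuvant cycle (1, 3, 5, etc; approximately every 8 weeks), and at the discretion of the Investigator", and at End of Treatment. Section 1.1 limits treatment: "The duration of treatment for each patient will be up to 34 weeks".

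Progression is still looked for afterwards. For the first 2 years after the last dose, Section 7.3.6 says "patients will be followed for progression every 2 months by telephone call, clinic visit, or medical records". It continues: "After 2 years have elapsed, patients will be followed every 6 months for progression by telephone call, clinic visit, or medical records". A scan is not needed to declare progression; under criterion d) of Section 7.3.4, "A diagnosis of clinical progression or deterioration may be made at the discretion of the treating physician".

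For OS, Section 8.4.7 censors at the "last study visit if the patient is still on treatment, or last long-term survival assessment where the patient was known to be alive". Long-term contacts therefore give follow-up time to OS non-events, but nothing says that they do so for PFS non-events.

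**The concern.** After treatment ends, a contact that finds progression or death enters the PFS analysis on its own date. A contact that finds the patient progression-free adds nothing, and the patient is censored back at the last tumor response assessment. If that is the last scheduled MRI, censoring falls at about month 8 however long the patient stayed free of progression.

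Whether time after treatment counts thus depends on what happens later. Kaplan-Meier estimation needs censoring to be unrelated to the later outcome, and here the rule itself creates the link. Beyond the last scan, the risk set consists mostly of patients who go on to have an event, and the curve falls too fast.

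At stake are the late PFS curve, the upper quartile and, if it lies beyond about 8 months, the median. PFS at each dose level is a stated secondary endpoint (Section 3), and OS and PFS are the only efficacy endpoints (Section 7.3).

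**Working it through.** The protocol gives no PFS figure to reproduce: no assumed median, event count or power. The check is of direction and size.

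**Inputs from the protocol.** Treatment up to 34 weeks, so the last scheduled scan is at L = 34 × 12/52.18 = 7.8 months. Accrual of 1 patient per 2 months (Section 8.4.10). Up to 30 patients (Section 1.1).

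**Assumptions not in the protocol.** Exponential PFS with a chosen true median; a chosen length of follow-up F; no scan after Week 34; follow-up contacts detect progression without error.

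**1. Ten patients by hand.** Progressions at 3, 4, 5, 6, 12, 15 and 20 months; three patients still progression-free at 30 months, last scan at 7.8 months. Both rules give 0.60 after month 6.
- Rule as written: 3 remain at risk after 7.8 months. Month 12: 0.60 × 2/3 = 0.40. Month 15: 0.40 × 1/2 = 0.20. Month 20: 0.
- Follow-up credited: 6 remain at risk. Month 12: 0.60 × 5/6 = 0.50. Month 15: 0.50 × 4/5 = 0.40. Month 20: 0.40 × 3/4 = 0.30.

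**2. Closed form, everyone followed to F.** After L, only patients with an event in (L, F] stay at risk, so the estimate tends to

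S_plan(t) = S(L) × [S(t) − S(F)] / [S(L) − S(F)].

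True median 12, S(L) = 0.637:
- F = 24, S(F) = 0.25: 12-month PFS = 0.637 × (0.50 − 0.25)/(0.637 − 0.25) = 0.411, against 0.50. The median solves S(t) = 0.25 + 0.5 × 0.387/0.637 = 0.554, giving 10.2 months instead of 12.
- F = 48, S(F) = 0.0625: 12-month PFS = 0.637 × 0.4375/0.5745 = 0.485, against 0.50. 24-month PFS = 0.637 × 0.1875/0.5745 = 0.208, against 0.25.

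True median 8, S(L) = 0.508:
- F = 24, S(F) = 0.125: 12-month PFS = 0.508 × (0.354 − 0.125)/(0.508 − 0.125) = 0.304, against 0.354. The median solves S(t) = 0.125 + 0.5 × 0.383/0.508 = 0.502, giving just under 8 months, so it is essentially unchanged.
- F = 48, S(F) = 0.0156: 12-month PFS = 0.508 × 0.338/0.492 = 0.349, against 0.354. 24-month PFS = 0.508 × 0.109/0.492 = 0.113, against 0.125.

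**3. Simulation with staggered entry.** 1000 trials per setting, 30 patients, protocol accrual rate, MRI at weeks 0, 10, 18, 26 and 34, then 2-monthly contacts, data cut 12 months after the last entry. Mean Kaplan-Meier PFS:

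| True median (months) | Time | True | As written | Follow-up credited |
|---|---|---|---|---|
| 7 | 12 months | 0.305 | 0.285 | 0.307 |
| 7 | 24 months | 0.093 | 0.065 | 0.090 |
| 10 | 12 months | 0.435 | 0.394 | 0.432 |
| 10 | 24 months | 0.189 | 0.129 | 0.188 |
| 15 | 12 months | 0.574 | 0.520 | 0.574 |
| 15 | 24 months | 0.330 | 0.213 | 0.326 |

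The typical estimated median (as written / follow-up credited) is 7.5/7.5, 9.5/10.4 and 12.5/14.7 months for true medians of 7, 10 and 15. At 6 months the curve is essentially unbiased (for example 0.662 against 0.660 with median 10). Cutting the data 24 months after the last entry reduces the bias without removing it: with median 15, 24-month PFS is 0.250 against 0.330.

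**The case against.** The strongest reply concerns the undefined term. PFS is based on RANO criteria, and follow-up includes clinic visits and records. A scan retrieved that way may reasonably be called a tumor response assessment, and footnote 1 allows scans at the investigator's discretion. A patient with a clear scan at month 24 would then be censored at month 24, and the asymmetry would remain mainly for deaths, clinical progression and contacts without imaging. This stands as a limit: under that reading the bias largely disappears. It does not settle the matter, because the text nowhere adopts that reading.

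Second, size. With a true median of 8 and everyone followed exactly 24 months, the formula gives 24-month PFS of 0% instead of 12.5%, and a reader might take that as the expected damage. The documents do not support it: the zero is forced by setting F = 24, whereas Section 7.3.6 follows patients for 2 years after the last dose and then continues. At 48 months the figure is 11.3%. The larger biases also need long medians. Section 1.1 cites a median survival of 14.6 months with standard therapy, so a median PFS of 15 is optimistic, although grade III and IDH-mutant patients are eligible.

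Third, precision. A 95% interval around 50% is about ±1.96 × √(0.25/12) = ±28 points with 12 patients and ±18 with 30, wider than most of these biases. True, but the bias is systematic and avoidable.

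Fourth, a telephone call can show that a patient is alive but not that RANO progression is absent. So different OS and PFS censoring is not itself an error, and crediting every contact could bias PFS upward. This stands and shapes the fix.

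Finally, a reader might infer that deaths without documented progression are censored, because the rule does not say *alive*. The preceding sentence makes death an event, so this is wording only. Nor can it be asserted that the schedule's long-term follow-up column contains no MRI: that row is not legible in the text at hand, and the schedule here rests on footnote 1 and Sections 4.1.5 and 7.3.

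**Conclusion.** The point holds in a conditional form. As written, events are accepted from any source at any time while non-events stop at the last tumor response assessment. Unless long-term follow-up evaluations count as such assessments, censoring depends on the later outcome and Kaplan-Meier PFS is biased downward after about 8 months.

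The size cannot be fixed from the documents. Under exponential PFS with no scans after Week 34, it runs from about half a percentage point at 12 months (median 8, 48 months of follow-up) to about 9 points (median 12, 24 months of follow-up). More follow-up shrinks it; longer true PFS enlarges it.

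PFS is secondary and Section 8.1 plans no hypothesis test, so the consequence is for interpreting late PFS and for using it to plan a later efficacy trial, not for the MTD. Section 8.4 lets the SAP prevail, but the protocol has stated this rule rather than left it open, so the SAP would have to replace it.

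**What to change.** Revise the censoring sentence in Section 8.4.7, or replace it in the SAP, so that events and non-events share one ascertainment. Either:

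- **(a)** censor patients who are alive and without progression at the last date on which progression status was evaluated and found negative, including long-term follow-up evaluations. The downside, to be stated, is that contacts without imaging may miss progression; or
- **(b)** for a scan-based RANO PFS, count only events within a stated window after the last tumor assessment, and censor everyone else at that assessment. If no later scans are available, this version says little beyond about 8 months.

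Name one as the main analysis and report the other as a sensitivity analysis. In either case, define which follow-up evaluations count as tumor response assessments and add the word *alive*.

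The cost is a sentence or two of text. Version (a) uses contacts that are already planned; version (b) needs only a choice of window.
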